OFFICIAL TITLE OF STUDY: Targeting Attention Orienting to Social Threat to Reduce Social Anxiety in Youth

NCT NUMBER: 03932032

DATE: 03-10-2026

[figure not shown]
PROTOCOL

The primary goal of this 2-site (Florida International U; Yale U) R01 project is to confirm attention bias modification treatment (ABMT) as an efficacious treatment for social anxiety disorder (SAD) in children and adolescents (i.e., “youth”) ages 10 to 14 years. We will randomize N=260 youths (130 each site) to 8 sessions of either ABMT or Neutral Control Task (NCT) delivered twice weekly for 4 weeks, with 160 trials per session. At pre-treatment (PRE), post-treatment (POST), and 6-month Follow-Up, we will assess the target, specifically, P1 amplitudes for socially threatening stimuli, and social anxiety symptom severity rated by independent evaluators (IEs), youths, and parents.

- Aim 1: Demonstrate target engagement. Hypothesis 1:** P1 amplitudes for socially threatening stimuli in the dot-probe task will be significantly lower at POST in the ABMT arm compared with the NCT arm.
- Aim 2: Demonstrate effects of ABMT on social anxiety symptom severity. Hypothesis 2a.** Social anxiety symptom severity rated by IEs, youths, and parents at POST will be significantly lower in the ABMT arm compared with the NCT arm. **Hypothesis 2b.** Youth ratings of state anxiety measured during a social evaluative stress task at POST will be significantly lower in the ABMT arm compared with the NCT arm.
- Aim 3: Demonstrate target validation. Hypothesis 3:** P1 amplitudes for socially threatening stimuli in the dot-probe task will mediate reductions in social anxiety symptom severity.
- Aim 4: Evaluate maintenance of target engagement, effects on social anxiety symptom severity, and target validation. Hypothesis 4:** Target engagement, effects on social anxiety symptom severity, and target validation will be maintained at 6-month Follow-Up evaluation.

APPROACH

See Figure 1 for the randomized controlled design and Table 1 for the measures administered at each assessment. Following parental consent and child assent, youths and parents will be administered interviews and questionnaires (see Measures) and youths will complete the dot-probe task while EEG/ERP data are collected (PRE). Youths will also be administered a measure of state anxiety immediately before a social stress task at PRE.

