Subjects will be randomized 1:1 to two study arms: ABMT or NCT. Subjects in each arm will complete 8 sessions over 4 weeks. Number and duration of sessions will be identical in both arms. We will collect data on the target variable (P1 amplitudes) and the outcomes (social anxiety symptom severity) from the youths and parents one week after treatment ends (POST). At POST, youths will also be re-administered a measure of state anxiety immediately before a social stress task. Six months after the POST assessment, youths and parents will once again be administered all measures including the dot-probe task while EEG/ERP data are collected and a social stress task (Follow-Up).

Subjects

Two-hundred sixty youths ages 10 to 14 years with SAD will be admitted to the study (n=130 at each site). **Inclusion Criteria.** (A) Be between ages 10 and 14 years; (B) meet DSM5 criteria for a diagnosis of SAD; (C) cease other psychosocial treatment; (D) presence of any coexisting psychiatric diagnoses must be of lesser severity than SAD; and (E) have no current psychotropic medication other than a stable dose of stimulant or non-stimulant medication for coexisting ADHD.

Exclusion Criteria. (A) meet for Autism Spectrum Disorder, Intellectual Disability, Bipolar Disorder, Tourette’s Disorder, Psychotic Disorders, or Substance Use Disorders; (B) show high likelihood of hurting themselves or others; (C) be a victim of undisclosed abuse requiring investigation/supervision by Social Services; (D) have a history of neurological illness, including seizures/epilepsy, or head injury with loss of consciousness ≥ 5 minutes; or (E) have an uncorrected vision or physical disability that interferes with their ability to see stimuli presented briefly on a computer screen or click a mouse button rapidly.

Interventions

ABMT. Subjects assigned to the ABMT arm will complete 2 ABMT sessions a week for 4 weeks, for a total of 8 sessions. At each session, subjects complete 160 ABMT trials. In each ABMT trial (see Figure 5 for an example trial of ABMT), following a fixation cross, 2 faces of the same actor (one angry, one neutral), one above the other, are presented for 500ms. Next, a probe (< or >) appears in the location of the neutral face. Subjects press the left or right mouse button to indicate the orientation of the probe (< or >). The probe remains on the screen until subjects respond. Neutral face location, actor, and probe type will be fully counterbalanced.

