We will conduct a full missing values analysis (MVA) in order to identify variables that are related to missingness; these variables will be included as auxiliary variables in any analysis models to reduce bias due to missingness. The proposed analysis methods (i.e., multilevel regression with maximum likelihood estimation) are robust to MAR (missing at random) or MCAR (missing completely at random) mechanisms, which will minimize impact of missingness and attrition. If there is evidence of MNAR (missing not at random) patterns, we will use appropriate methods. We will assess whether data meet all assumptions of analysis (multivariate normality, outliers) prior to analyses. We will adjust for any violations using robust methods (such

as using bootstrap standard errors). We will evaluate group differences in potential covariates (e.g., sex, pubertal status, race/ethnicity, P1 amplitudes, social anxiety severity, comorbid diagnoses, treatment utilization) prior to analyses to assess randomization and will include these variables in models as needed. Analyses will use the combined dataset from the two sites. Site will be included as a covariate to adjust for any clustering effects. In general, mixed models (also called multi-level or growth models) will be used to assess change in outcome variables over time within each treatment arm. Preliminary models will include time, group, and the time x group interaction, which indicates whether the groups differ in their change over time (on average). We will evaluate models with random intercepts (allowing individuals to vary in their mean levels of the outcome) and random slopes (allowing individuals to vary in their change over time) and choose the best model using likelihood ratio (LR) tests. We will also evaluate models with non-linear change with respect to time (e.g., $\ln[\text{time}]$) and choose the best model using LR tests. We will use a Holm adjusted modified Bonferroni method for controlling experimentwise error rates; it is more powerful than traditional Bonferroni or Scheffe methods.¹⁷¹

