Aim 1: Demonstrate target engagement. The effect of treatment group on P1 amplitudes will be assessed using a mixed model with P1 amplitudes as the (repeated) outcome =; group, time, and the group x time interaction will be included as predictors. The “time” variable will be centered at POST assessment, allowing us to evaluate group differences at that wave. The group effect represents the difference between groups at the POST assessment; significantly lower scores in the ABMT arm compared with the NCT arm would confirm target engagement.

Aim 2: Demonstrate effects of ABMT on social anxiety symptom severity. The same general procedures described in Aim 1 will be applied to Aim 2 data analysis. The effect of treatment group on social anxiety symptom severity will be assessed using a mixed model with social anxiety symptom severity as the repeated measure; group, time, and the group x time interaction will be included as predictors. The “time” variable will be centered at POST assessment, allowing us to evaluate group differences at that wave. Of interest is whether the contrast between study arms is statistically significant. The group effect represents the difference between groups at the POST assessment; significantly lower scores in the ABMT arm compared with the NCT arm would demonstrate the efficacy of ABMT. We will use the same analytic approach when examining subjects’ levels of state anxiety (STAI-C-S) before the TSST.

Aim 3: Demonstrate target validation. We will examine changes in P1 amplitudes as a mediator of the social anxiety reduction effect of ABMT using an extension of the approach described in Aims 1 and 2, within a larger structural equation modeling (SEM) framework. Within a single model, change in P1 amplitudes will be modeled as in Aim 1 and change in social anxiety symptom severity will be modeled as in Aim 2. In addition, the effect of the P1 amplitudes slope on both (a) the group effect on social anxiety symptom severity and (b) the group x time interaction on social anxiety symptom severity will be included. These additional effects (“paths”) will allow us to evaluate how change in P1 amplitudes relates to group differences in change in social anxiety symptom severity across the assessment waves, including at POST. Statistical significance of the mediated effect will be assessed using Monte Carlo methods.

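### Reading the group coefficient at POST as the POST difference is safe only if the time model is saturated, and the plan does not ensure that; permitted codings can shrink a maintained effect to about half

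*Combined protocol and SAP*

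**What the plan says.** The Aim 1 paragraph of the Statistical Analysis Plan specifies a mixed model with group, time and group by time. Aim 2 uses the same model. In both, the time "variable will be centered at POST assessment, allowing us to evaluate group differences at that wave", and the group coefficient is then interpreted as the arm difference at POST. It is the test for Hypotheses 1, 2a and 2b.

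The general paragraph of the Statistical Analysis Plan calls this set of terms preliminary. It compares random-intercept and random-slope models by likelihood ratio (LR) tests and adds: "We will also evaluate models with non-linear change with respect to time". Its only example is the logarithm of time, again to be chosen by LR test.

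On timing, the opening of the Protocol names three assessments: "At pre-treatment (PRE), post-treatment (POST), and 6-month Follow-Up, we will assess the target". The Approach section gives the spacing: "Subjects in each arm will complete 8 sessions over 4 weeks", POST is "one week after treatment ends (POST"), and "Six months after the POST assessment, youths and parents will once again be administered all measures". Aim 4 is described as a variant of the Aim 1 and 2 analysis, with four waves for most outcomes and three for state anxiety.

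The text does not say which waves enter the Aim 1 and 2 models, in what unit time is measured, or what the fourth wave is. Figure 1 and Table 1 of the Approach section are not reproduced in the text reviewed here and may define that wave. No section specifies time as categorical.

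**The concern.** Centring moves the origin of a numeric variable. It does not make the model fit the data at that origin. With three or more waves and one time term, each arm's mean is forced onto a line (or one chosen curve). The group coefficient is then the gap between the two fitted lines at POST, a weighted mix of the arm differences at all waves.

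Two features of the plan suggest that more than two waves are intended. Random slopes cannot be tested on two waves: an intercept variance, a slope variance, their covariance and a residual variance make four parameters, against three observable variances and covariances. Also, every time shape fits two waves identically, so there would be nothing for an LR test to choose. The Aim 3 paragraph, which builds on the Aim 1 and 2 models, also speaks of change over the assessment waves with POST as one of them.

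If Follow-Up does enter, the pattern that Hypotheses 1, 2 and 4 jointly predict is an effect present at POST and maintained six months later. That is a step followed by a plateau, which a straight line cannot follow. At stake are the size and power of the confirmatory tests, and whether their estimand is fixed before the data are seen.

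**Working it through.** The documents give no effect size, standard deviation, alpha, power or dropout, so there is no planned figure to reproduce.

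**Inputs from the documents.** POST falls about 4 + 1 = 5 weeks after PRE, and Follow-Up about 26 weeks after POST. The waves are therefore at weeks 0, 5 and 31. The gap between PRE and the first session is not stated, so PRE-to-POST gaps of 4 to 8 weeks were also tried. With 260 youths and "Subjects will be randomized 1:1 to two study arms", there are 130 per arm.

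**Weights of the fitted value at POST.** With complete data and a random intercept, with or without a random slope, generalised and ordinary least squares give the same weights:

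w(t) = 1/3 + (5 − 12)(t − 12)/554,

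where 12 is the mean of 0, 5 and 31, and 554 = 12² + 7² + 19².

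- PRE: 1/3 + (−7)(−12)/554 = 0.485
- POST: 1/3 + (−7)(−7)/554 = 0.422
- Follow-Up: 1/3 + (−7)(19)/554 = 0.093

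PRE carries more weight than POST in the coefficient that is read as the POST difference. For true differences (0, d, d), the coefficient is 0.422d + 0.093d = 0.515d. For PRE-to-POST gaps of 4 to 8 weeks it is 0.510d to 0.534d. The line is exact only if the difference grows in proportion to time, to (31/5)d = 6.2d at Follow-Up.

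**Other permitted codings, for the same maintained effect**

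| Waves and time form | Share of d recovered |
|---|---|
| PRE and POST only | 1.00 |
| Three waves, linear in weeks | 0.52 |
| Three waves, linear in wave number | 0.67 |
| Three waves, ln(months+1) | 0.59 |
| Three waves, ln(weeks+1) | 0.68 |
| Three waves, ln(days+1) | 0.78 |
| Three waves, quadratic with group interaction | 1.00 |

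**The selection step.** Time centred at POST is negative at PRE and zero at POST, and time from PRE is zero at PRE, so ln(time) needs an offset that the plan does not give. Linear and ln(time) models have the same number of parameters and neither contains the other, so an ordinary LR test cannot compare them. Choosing the one with the higher likelihood does not cure the problem. In simulations (d = 0.40 SD, correlation 0.5, 1,000 replicates for each of five common trends), ln(weeks+1) was preferred over linear in 83% to 100% of runs, and the chosen model recovered 0.65d to 0.69d.

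**Power (illustrative).** Assumed: two-sided 0.05 without Holm adjustment, no dropout, equal correlation r between waves. The weights sum to 1, so the variance of the weighted mean in SD units is (1 − r)Σw² + r. For d = 0.40 and r = 0.5, linear in weeks:

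- Σw² = 0.422, variance 0.5 × 0.422 + 0.5 = 0.711, SD 0.843
- standard error 0.843 × √(2/130) = 0.105
- z = 0.515 × 0.40/0.105 = 1.97, power about 0.50

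For a direct POST contrast: z = 0.40/√(2/130) = 3.23, power about 0.90.

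| d (SD) | POST contrast | Linear in weeks, r = 0.3 to 0.7 | Wave number, r = 0.3 to 0.7 |
|---|---|---|---|
| 0.35 | 0.81 | 0.47 to 0.36 | 0.73 to 0.56 |
| 0.40 | 0.90 | 0.58 to 0.45 | 0.84 to 0.67 |
| 0.50 | 0.98 | 0.77 to 0.63 | 0.96 to 0.85 |

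**The case against.** A reader might infer that the planned test is not the POST difference and will recover only half of a real effect. The documents do not support that as a statement about the plan, for three reasons.

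- Linear time is not fixed. The general paragraph calls the model preliminary and allows non-linear change, with the logarithm only as an example. A quadratic is nested over the line, so an LR test is valid for it. Interacted with group, it saturates three waves. For (0, d, d) with d = 0.40 and r = 0.5, the curvature contrast (−26, 31, −5) has length √1662 = 40.8. This gives z = (26 × 0.40/40.8)/√(0.5 × 2/130) = 2.91, or about 83% power, so the plan's procedure could well reject the line. But the plan neither names a quadratic nor says that an added time term would interact with group.
- The waves are not stated. Aims 1 and 2 may use PRE and POST only, in which case the coefficient is exact. Follow-Up could also be the wave that Aim 4 adds to three waves ending at POST. With an assumed mid-treatment wave two or three weeks before POST, a line then recovers between 0.76d and 1.16d, depending on how much of the effect is present by then. Neither reading is settled by the text.
- The time unit is not stated, and one half is the low end of the three-wave codings tabulated.

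A reader might also infer a risk of false efficacy, or a bias from chance imbalance at PRE. Under randomisation the expected imbalance is zero. With no difference at any wave the expected coefficient is zero too. In a single trial, at r = 0.5, a unit of PRE imbalance carries 0.485 + 0.5 × (0.422 + 0.093) = 0.74 into the linear estimate. An unconstrained POST contrast still carries 0.50, so a categorical model reduces this without removing it.

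What stands: the plan asserts that the coefficient is the POST difference, and several codings that it allows make that assertion false.

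**Conclusion.** The point holds in conditional form. If Follow-Up data enter the Aim 1 and 2 models and the mean is not saturated in time, the group coefficient need not equal the POST difference. For an effect present by POST and then maintained, it recovers about 0.52d to 0.78d under the three-wave linear and logarithmic codings tabulated. It recovers the full effect if only PRE and POST are used, or if a quadratic with group interaction is fitted to three waves. The recovery figures rest on complete data, a random-intercept or random-slope covariance, and the visit spacing in the Approach section. The power figures also rest on an assumed effect size, correlation and alpha.

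The harm is bias toward zero, lost power and a confirmatory estimand that depends on a data-driven choice, part of which an ordinary LR test cannot make. This is more than missing detail, because a natural reading of the plan gives an attenuated confirmatory test.

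**What to change.** For the confirmatory tests, prespecify one model: visit as a categorical factor covering every planned wave, group by visit, unstructured within-youth covariance, and site as covariate. Read Hypotheses 1, 2a and 2b from the POST contrast, and the Aim 4 group comparisons from the Follow-Up contrast. With complete data the POST contrast recovers d in full whatever happens at the other waves.

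Drop LR-test selection of the time form for these tests; growth curves can remain exploratory. State which waves enter each aim. Reconcile the four waves in Aim 4 with the three named in the opening of the Protocol and the Approach section, so that the visit factor has the right number of levels.

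The cost is small but is more than wording. The model has a few extra mean and covariance parameters, which matter little with 260 youths. Aim 3 and its Aim 4 variant use the slope of P1 amplitude as the mediator, and a categorical model has no slope. Those analyses must either keep their own stated growth model or define P1 change as the PRE-to-POST change. No new data are needed.

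### Aims 1 and 2 do not commit to adjusting the POST contrast for PRE: the arm difference at PRE is left free and PRE enters as a covariate only after a between-arm comparison

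*Combined protocol and SAP*

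**What the plan says.** The protocol overview and the section on subjects give 260 youths, allocated 1:1, hence 130 per arm. The PRE values exist by design: "At pre-treatment (PRE), post-treatment (POST), and 6-month Follow-Up, we will assess the target", and symptom severity is assessed at the same times.

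For Aim 2 the SAP uses "a mixed model with social anxiety symptom severity as the repeated measure", in which "group, time, and the group x time interaction will be included as predictors". Aim 1 has the same structure for P1. Time is centered at POST, and "The group effect represents the difference between groups at the POST assessment". Nothing holds the arms equal at PRE, and PRE is not a standing covariate.

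The general methods paragraph of the SAP always includes site. Other candidate covariates, given as examples, include "P1 amplitudes, social anxiety severity, comorbid diagnoses, treatment utilization". The plan compares the arms on these "prior to analyses to assess randomization and will include these variables in models as needed". It names no test, threshold or other criterion.

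The same paragraph allows random intercepts or slopes and linear or non-linear time, chosen by likelihood ratio tests. Aims 1 and 2 do not list the waves that enter. Aim 4 refers to four waves for most outcomes, whereas the protocol describes three assessments.

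**The concern.** A mixed model that contains PRE looks as if it adjusts for PRE. With a free arm difference at PRE, it does not. The PRE value is probably the best predictor of the POST value that this trial collects, and the plan uses it in the POST contrast only if the arms happen to look different.

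That rule has two weaknesses. In a randomised trial a PRE difference between arms is chance, so comparing the arms does not show which covariates predict the outcome. And because no criterion is stated, the confirmatory model depends on the data. At stake are the precision of the Aim 1 and Aim 2 contrasts and of their Aim 4 variants, and the influence of chance PRE imbalance on them. If a single slope in time is chosen, the size of the estimated effect is also at stake.

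**Working it through.** **Inputs.** From the documents: 130 per arm; POST one week after four weeks of treatment; Follow-Up six months after POST. Assumed, because the documents do not give them: two-sided 0.05 for a single test (before Holm), effect d = 0.35 SD, PRE-POST correlation r, no dropout, PRE at week 0. POST is then week 5 and Follow-Up about week 31. The plan gives 260 without an effect size, SD, power or dropout, so that figure cannot be reproduced. For scale, 130 per arm detects (1.96 + 0.84) × √(2/130) = 0.347 SD with 80% power, unadjusted.

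**1. What the group coefficient is.** With PRE and POST waves and complete data, group, time and their interaction fit all four arm-by-wave means exactly. The group coefficient at POST is then the raw difference in POST means. In 150 simulated trials (r=0.6) the fitted mixed model differed from the raw difference by at most 3e-15. Its mean SE was 0.123, against 0.099 with PRE as a covariate. The variance ratio was 0.65; theory gives 1 − 0.6² = 0.64.

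**2. What always adjusting is worth.** The variance factor is 1 − r² and the equivalent unadjusted sample is 260/(1 − r²). Power is from simulation at d = 0.35; unadjusted power is about 0.80.

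| r | variance factor | equivalent N | power, always adjusted |
|---|---|---|---|
| 0.4 | 0.84 | 310 | 0.86 |
| 0.5 | 0.75 | 347 | 0.90 |
| 0.6 | 0.64 | 406 | 0.94 |
| 0.7 | 0.51 | 510 | 0.98 |

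**3. Adjusting only after a flag.** For a two-sided imbalance test at level a with critical value c, the share of the available variance reduction that is lost is (1 − a) − 2cφ(c), whatever r is.
- a = 0.05: 0.95 − 2 × 1.96 × 0.0584 = 0.72
- a = 0.10: 0.56
- a = 0.20: 0.35

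At a = 0.05, simulated power is 0.81 at r=0.4 and 0.82 at r=0.6. At r=0.6 the rejection rate under no effect is 0.041.

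**4. How imbalance carries through.** The SE of an arm difference is √(2/130) = 0.124 SD. A PRE difference of 0.20 SD gives z = 0.20/0.124 = 1.61, which a 0.05 test does not flag. At r=0.6 it shifts the expected POST difference by 0.6 × 0.20 = 0.12 SD, about one SE.

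**5. Three waves with one slope.** At weeks 0, 5 and 31 the mean is 12 and the sum of squared deviations is 144 + 49 + 361 = 554. The fitted POST difference weights each wave by 1/3 + (5 − 12)(t − 12)/554.
- PRE: 0.333 + 84/554 = 0.485
- POST: 0.333 + 49/554 = 0.422
- Follow-Up: 0.333 − 133/554 = 0.093

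The PRE difference enters with a positive weight, opposite in sign to a baseline adjustment. An effect that is zero at PRE and constant afterwards is estimated as 0.422 + 0.093 = 0.52 of its size. Coding waves 0, 1, 2 gives 0.67, and ln(weeks + 1) gives 0.68. At r=0.5 the variance is 0.67 to 0.71 of the raw POST contrast, so the nominal SE is smaller. Signal over SE is still only 0.61 to 0.83 of the raw contrast, against 1.155 with PRE adjustment.

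**6. A trap in the remedy.** Suppose the arms are given a common PRE mean but one linear slope is kept. With equal correlation r between waves and k = r/(1 + 2r), the slope for an effect of (0, 1, 1) is (36 − 72k)/(986 − 1296k), and the POST estimate is five times that.
- r=0.4: k = 0.222, 5 × 20/698 = 0.14
- r=0.7: k = 0.292, 5 × 15/608 = 0.12

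This is worse than the 0.52 above, so a common PRE mean needs categorical time.

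**The case against.** The strongest reply is that the SAP describes growth models, not a saturated model. With three or more waves and one slope, the group effect at POST is not the raw POST difference, and the variance figures in steps 2 and 3 do not describe it. That stands. Those figures hold only for two waves or categorical time with complete data. Under the other reading the loss is dilution of the effect (step 5), and that reading does not adjust for PRE either. When POST values are missing at random, maximum likelihood does draw some information from PRE, but this does not replace adjustment.

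Several stronger readings are tempting, and the documents do not support them.
- A reader might infer that most of the available precision is given up. That depends on the flagging threshold: 72% of the gain is lost at 0.05 but 35% at 0.20, and the SAP states none. Even a formal imbalance test is an inference from the wording.
- A reader might infer that every hypothesis loses precision. Hypothesis 3 is a mediation test built on the P1 slope and does not rest on an unadjusted POST contrast.
- A reader might infer that adjusting for treatment utilization biases Aim 4. That follows only if it is measured after randomisation. The SAP gives no timing, and its place in a check of randomisation suggests a baseline variable.
- A reader might infer that PRE severity would be both covariate and first response in one model. P1 and severity could each serve in the other's model; the SAP does not say.

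**Conclusion.** The point holds as one of efficiency and prespecification. The plan collects PRE values but does not commit to using them to adjust the POST contrast, and it leaves the time coding, the wave set and the covariate rule open.

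Under the saturated reading, always adjusting removes 16% to 49% of the variance for r of 0.4 to 0.7. At an assumed 0.35 SD effect, power rises from about 0.80 to 0.86 at r=0.4 and 0.94 at r=0.6. An assumed 0.05 flag recovers little of that. Under a single-slope reading with three waves, an effect constant after PRE is estimated at roughly 0.5 to 0.7 of its size. The documents give neither the correlation nor the effect size, so the gain cannot be fixed more closely.

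A reader might go further and call the planned test invalid. That is not supported: the unadjusted saturated contrast is unbiased on average under randomisation, and in the simulation the flag-triggered rule was conservative (0.041) rather than liberal.

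**What to change.** For Aims 1, 2 and 4, prespecify one model with categorical time that always conditions on PRE. Either form serves:
- POST and Follow-Up as responses, with the PRE value of the outcome and its interaction with visit as covariates; or
- PRE, POST and Follow-Up as responses, with a common PRE mean across arms and a separate arm effect at each later visit.

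Do not combine a common PRE mean with a single slope in time (step 6). State which waves enter each model, and reconcile the four waves in Aim 4 with the three assessments in the protocol.

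Replace the conditional covariate rule with a fixed list measured before randomisation: site, the PRE value of the outcome, and a few others chosen in advance. Do not adjust for treatment utilization measured after randomisation; report it by arm.

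The cost is SAP wording, settled before anyone sees outcomes by arm. PRE measurement is already part of the design, so no added assessment or participant is needed.

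### The Aim 3 paths, as written, specify effect modification by P1 slope; the P1-to-severity path and the product that defines the mediated effect are not stated

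*Combined protocol and SAP*

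**What the plan says.** Hypothesis 3 in the protocol states that "P1 amplitudes for socially threatening stimuli in the dot-probe task will mediate reductions in social anxiety symptom severity". The SAP's Aim 3 repeats the intent: "We will examine changes in P1 amplitudes as a mediator of the social anxiety reduction effect of ABMT", within one structural equation model.

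The model has two parts and two additions. For the parts, "change in P1 amplitudes will be modeled as in Aim 1 and change in social anxiety symptom severity will be modeled as in Aim 2". The additions are "the effect of the P1 amplitudes slope on both (a) the group effect on social anxiety symptom severity" and, as the second path, "b) the group x time interaction on social anxiety symptom severity will be included".

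Under Aim 2, with time centred at POST, "The group effect represents the difference between groups at the POST assessment". Aim 1 defines the term in the same way.

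The next sentence of Aim 3 interprets the added paths as relating P1 change to group differences in severity change. Aim 4 uses the same construction for Follow-Up. The mediated effect is to be tested by Monte Carlo methods, but the SAP does not say which coefficients are multiplied.

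**The concern.** Mediation needs three things: an effect of group on P1 change (a), an effect of P1 change on the same youth's severity (b), and a test of a×b with the direct group effect in the model. The SAP supplies a through the Aim 1 part and the direct effect through the Aim 2 part. It does not write b.

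What it writes has a different target. The group effect is a between-arm contrast, not a quantity that each youth has. Letting a youth-level slope act on that contrast asks whether the ABMT benefit differs between youths with different P1 change. In a regression this is a P1-slope-by-group term (and, for the second path, P1-slope-by-group-by-time).

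At stake is the target-validation claim, in Aim 3 and again in Aim 4. Two analysts following the text could fit different models and reach opposite conclusions, and one of those models does not address Hypothesis 3.

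**Working it through.** **No figure to reproduce.** The documents give N = 260 and state that "Subjects will be randomized 1:1 to two study arms: ABMT or NCT", so about 130 per arm. They give no effect size and no power for Aim 3. The effect sizes below are assumptions in SD units, and the error rate is taken as two-sided 0.05.

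**Model for the check.** G is the arm (1 = ABMT), M the youth's P1 slope, Y the severity change.
- M = a·G + e, with e of variance 1.
- Y = b·M + e', with e' of variance 1 − b².
- There is no direct effect and b is the same in both arms, so this is full mediation.

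**Three analyses a reader could fit.**
1. Usual mediation: Y on G and M; test a×b.
2. Literal path with the P1 main term: Y on G, M and G·M; test the G·M coefficient.
3. Literal path without the P1 main term: Y on G and G·M (M centred); test a×(G·M coefficient).

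**What each added coefficient estimates.** In (1) it is b. In (2) it is b in ABMT minus b in NCT, which is zero under full mediation with equal b. In (3) the NCT arm is fitted by its mean alone and ABMT by its own line, so the coefficient is b in the ABMT arm, estimated from half the sample.

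**Approximate arithmetic at a = -0.5, b = 0.3.**
- Path a: SE = √(2/130) = 0.124; |z| = 0.5/0.124 = 4.03; power = Φ(4.03 − 1.96) = 0.981.
- (1) b: SE = √(0.91/260) = 0.0592; z = 0.3/0.0592 = 5.07; power = 0.999. Both significant: 0.981 × 0.999 = 0.98.
- (2) G·M: expectation 0, SE = √(0.91 × 2/130) = 0.118; rejection = 0.05.
- (3) G·M: the residual variance averages 0.91 (ABMT) and 0.91 + 0.09 = 1.00 (NCT), giving 0.955; SE = √(0.955/130) = 0.0857; z = 0.3/0.0857 = 3.50; power = Φ(3.50 − 1.96) = 0.938. Both significant: 0.981 × 0.938 = 0.92.

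**Simulation** (1,500 trials per setting, Monte Carlo intervals for the products), share of trials significant under full mediation:

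| N | a | b | (1) a×b | (2) G·M, main term kept | (3) a×G·M, no main term |
|---|---|---|---|---|---|
| 260 | -0.35 | 0.3 | 0.79 | 0.05 | 0.72 |
| 260 | -0.5 | 0.3 | 0.98 | 0.05 | 0.92 |
| 260 | -0.5 | 0.5 | 0.98 | 0.04 | 0.98 |
| 208 (20% loss assumed) | -0.35 | 0.3 | 0.69 | 0.05 | 0.59 |
| 208 | -0.5 | 0.3 | 0.93 | 0.06 | 0.81 |
| 208 | -0.5 | 0.5 | 0.95 | 0.05 | 0.95 |

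Testing a×G·M with the main term kept gives 0.03 to 0.06, so forming a product does not rescue (2).

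**The opposite error.** Let the P1–severity slope be -0.2 in NCT and +0.2 in ABMT, with a = -0.5. The arm-specific products are -0.5 × (-0.2) = +0.10 and -0.5 × 0.2 = -0.10, which average zero. The G·M coefficient is 0.4 with SE √(0.96 × 2/130) = 0.122, so z = 3.29 and power is about 0.91. The simulation gives 0.90 for the interaction and 0.05 for a×b. Analysis (2) would report a finding here, and it would concern a difference between arms, not an average mediated effect.

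**The case against.** The strongest reply is that the paragraph plainly intends mediation. It calls P1 change a mediator, places it in a structural equation model, brings in group-to-P1 and group-to-severity through Aims 1 and 2, and names a test of the mediated effect. No moderation hypothesis appears anywhere. A fixed between-arm coefficient cannot receive an ordinary path, so the two targets may be loose wording for the severity intercept (the level at POST) and the severity slope.

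Much of this stands. The intent is mediation, and only the b path and the product are open. But the kind reading works by replacing the stated targets with others. The SAP uses the vocabulary of individual intercepts and slopes in its general section and does not use it in Aim 3. The group-differences wording also recurs in the next sentence and in Aim 4, so it is not one slip.

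A reader might infer more: that the SAP tests moderation and not mediation, so full mediation would be missed. The documents do not support that. Detection falls to about 5% only if a P1 main term is fitted, so that b is estimated, and then left out of the mediation test. The SAP does not say this. With no main term, which is closer to what is listed, the interaction coefficient picks up b and most of the power remains.

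It is also fair that the simulation uses a single change score and assumed effects, not the planned repeated-measures model. It shows that the readings test different quantities; it does not predict the trial's power.

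**Conclusion.** The point holds as a specification fault. The stated paths are effect-modification terms, while the P1-slope-to-severity path and the product are missing from the text. Under full mediation at the assumed a = -0.5, b = 0.3 and N = 260, detection is about 98% for a×b, about 92% on the literal reading without a P1 main term, and about 5% on the literal reading with the main term and only the interaction tested. Under a pure arm difference in the P1–severity slope, the interaction test with the main term kept is significant in about 90% of trials and a×b in about 5%.

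The contrast between the readings is structural and does not depend on the particular effect sizes. The exact percentages do depend on them, on equal b in both arms (for the first set) and on a two-sided 0.05 level. No sample-size or power figure in the documents is affected, and neither are the analyses of Aims 1 and 2.

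**What to change.** In the SAP, Aim 3:
- Replace the two added paths with P1 slope to the youth's severity intercept (time centred at POST) and P1 slope to the youth's severity slope. Keep the direct group effects on both.
- Define the mediated effect as (group to P1 slope) × (P1 slope to severity), with a Monte Carlo 95% interval, and say that this product is the test of Hypothesis 3.
- List any P1-slope-by-group term separately, as a check that the P1–severity path is the same in both arms, and not as evidence of mediation.

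In Aim 4, use the same definition with time centred at Follow-Up.

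The cost is rewording a few sentences. No new data or visits are needed. The change should be made and dated before the mediation analysis is run.
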